6.4.4.1 For M2951	Text was added to direct sites to consult with Medical Monitor if participants OLE predose or OLE baseline value is abnormal and/or below criteria	Provide direction to sites to consult with Medical Monitor regarding potential withdrawal, continued participation in study, additional monitoring, and retesting
6.4.4.1 For M2951 Only	The stopping criteria was adjusted for AST, ALT and bilirubin.	Updated liver enzyme stopping criteria to ensure the safety of the patients within the study.
Protocol History	Amendment 3 date updated.	To correct for consistency and accuracy.
7.1.3 Supplemental Safety Visits	Text was aligned to Table 2 for the additional visits for liver enzyme monitoring.	Increased liver monitoring was added following an urgent safety measure.
7.4.3	Added ESR to hematology evaluations	Correct omission
Sponsor Responsible Persons not Named on the Cover Page	Clinical trial leader was updated.	Personnel change.

Section # and Name	Description of Change	Brief Rationale
Appendix II: Total Blood Volume	Blood volume for the Open-label Extension Period was updated.	Blood volume was recalculated due to addition of assessments for the additional visits.

Amendment #3

Rationale

The protocol was revised to include recommendations from the Czech Republic Regulatory Authority on reinitiating IMP following increase in AST, ALT, or bilirubin to Grade 2.

Major Scientific Changes

The key reasons for Amendment 3 was to include recommendations from the Czech Republic Regulatory Authority on reinitiating IMP following increase in AST, ALT, or bilirubin to Grade 2.

Section # and Name	Description of Change	Brief Rationale
6.4.4.1 For M2951 Only	Amended instructions for reinitiating IMP following increase in AST, ALT, or bilirubin to Grade 2.	To include the recommendations from the Czech Republic Regulatory Authority

Amendment # 2

Rationale

The protocol was revised to include the recommendations from the Czech Republic Regulatory Authority to provide clarification to guidelines on withholding or permanent withdrawal of IMP, remove interim/futility analyses since primary analyses could be reached earlier due to fast recruitment, update the visit schedule according to the Modification of Visit Schedule for Monitoring of Liver Function Tests based on IDMC recommendations (16 April 2018), clarify that monthly urine pregnancy testing would occur at all sites in all countries, as well as other administrative changes.

Major Scientific Changes

Changes to the protocol were made to include the recommendations from the Czech Republic Regulatory Authority, include clarification on urine pregnancy testing for all sites, modify the supplemental safety visit schedule in the Schedules of Assessment based on the visit schedule memo issued to sites (16 April 2018), include a table on withholding and permanent withdrawal of IMP.

The key reasons for Global Amendment 2, Protocol Version 3.0, are summarized below:

• Remove Futility analyses (also referred to as interim analyses);

- Remove 2-week additional safety visits after Week 16 and update to a monthly (4-week) schedule;
- Clarify that phone calls for confirmation of home pregnancy testing is required only if urine pregnancy tests are completed at home;
- Include monthly urine pregnancy tests for all sites in all countries during the main study and OLE period;

- Update Section 5.6.1 to reference to Section 6.4.4 and add a table (in Section 6.4.4.1) with guidelines on withholding and withdrawal of IMP;
- Add sub bullets to Section 6.4.4.1 and 6.4.4.2 for increased clarity on management of laboratory evaluation abnormalities;
- Update Section 6.4.4.2 to match SmPC for Tecfidera;
- Include a new Table 6 to provide guidelines for withholding and modification of IMP;
- Update Table 7 (previously Table 6) to include a superscript to the footnote on urine microscopy.

Amendment #1

Rationale

For Poland only, a local amendment (Version 1.1) was created to provide additional at-home pregnancy testing at the request of the Polish Health Authority. The protocol was further revised to include the changes from the local Poland amendment, recommendations from the IDMC meeting on 05 October 2017, and to add an optional Long Term Open-label Extension Period.

Major Scientific Changes

The key reasons for Global Amendment 1, Protocol Version 2.0, are summarized below:

- Addition of 2-week safety visits for chemistry monitoring (including ALT, AST, alkaline phosphatase, GGT, and bilirubin) until the IDMC determines the optimum monitoring interval for participant randomized to the M2951/placebo arm;
- Addition of a comprehensive hepatic panel for participants randomized to the M2951/placebo arm for whom withdrawal criteria are met or who permanently discontinue dosing because of elevated transaminases;
- Addition of blood tests (ESR, hsCRP, and fibringen) for all participants at any 1 point during the trial;

- Addition of Open-label extension period, with modifications to planned trial period, addition of objective and endpoints, addition of statistical analyses and analysis set, addition of informed consent prior to participation, and clarification that there will be a second clinical trial report;
- Addition of CCI endpoints and statistical analyses;

\mathbb{CC}

• Clarification that separate informed consent will be collected for the MRI dummy run;

• Clarification that blood pressure will be collected in a semisupine position;

BMI Body Mass Index

BOA **Biostatistics Outputs Assembly**

CCI

CCI

Business Continuity Plan BCP

CFB Change from Baseline

CIconfidence interval

CTP Clinical Trial Protocol

DBP Double-blind period

DMT Disease Modifying Therapy

Exposure Adjusted Incidence Rate **EAIR**

electronic Case Report Form eCRF

ECG Electrocardiogram

EDSS Expanded Disability Status Scale

EEA European Economic Area

EOT End of Treatment FA Final Analysis

Gd+ Gadolinium-positive

GGT Gamma-Glutamyl Transferase

GI Gastrointestinal

IA Interim Analysis IAP Integrated Analysis Plan

Ig Immunoglobulin

IMP Investigational Medical Product

IPD Important Protocol Deviation

IV Intravenous

IWRS Interactive Web Response System

LLN Lower limit of normal

CCI

MedDRA Medical Dictionary for Regulatory Activities

mITT Modified Intention to Treat

MMRM Mixed Effect Model for Repeated Measures

MRI Magnetic Resonance Imaging

MS Multiple sclerosis
NB Negative binomial

NCI-CTCAE National Cancer Institute – Common Terminology Criteria for Adverse

Events

OLE Open-label extension

PA Primary Analysis

CC

Pdev Protocol deviation

CCI

PT Preferred Term

QD Once daily

Q1 25th Percentile Q3 75th Percentile

RMS Relapsing multiple sclerosis

RoW Rest of the World SAF Safety Analysis Set

SAF-OLE Safety Open-Label Extension Analysis Set

SAF-SWOLE Safety Switch Open-Label Extension Analysis Set

SCR Screening Analysis Set

SD Standard Deviation

SDTM Study Data Tabulation Model

SE Standard Error

CCI

SMC Safety Monitoring Committee

SOC System Organ Class

SPMS Secondary progressive multiple sclerosis

TEAE Treatment Emergent Adverse Event

TBILI Total Bilirubin

TLF Table/Listing/Figure

ULN Upper Limit of Normal

VS Vital signs

WHO-DD World Health Organization Drug Dictionary

4 Modification History

Unique Identifier for IAP Version	Date of IAP Version	Author	Changes from the Previous Version
1.0	25 April 2024	PPD	NA – first version
2.0	03 June 2024	PPD	Section 17.3: Add Kaplan-Meier plot for time to first increase in ALT ≥ 3, update analysis to include DBP + OLE Section 16.3: added two more percentiles summary (35th, 40th) in the KM estimates of the cumulative probability of experiencing qualified relapse

5 Purpose of the Integrated Analysis Plan

The purpose of this Integrated Analysis Plan (IAP) is to document technical and detailed specifications for the Final Analysis (FA) of data collected for protocol MS200527-0086 considering the early termination of the study; the primary endpoints of the phase 3 MS200527_0080 and MS200527_0082 studies were not met). The IAP is based upon Section 8 (Statistics) of the trial protocol dated 06 July 2023 (Version 8.0) and is prepared in compliance with International Conference on Harmonization E9.

This FA data report will include summaries of participant disposition, demographics, baseline characteristics, medical history, previous and concomitant medications, treatment exposure, efficacy evaluations, adverse events (AEs), deaths, selected laboratory parameters, vital signs, ECGs, and other endpoints related to safety monitoring up to the end of the study.

6 Objectives/Endpoints of the Final Analysis

The objective of the OLE Period of this study is to evaluate the long-term safety, efficacy, and HRQoL of M2951 for an additional 8 years, at an initial dose of 75 mg once daily which was eventually switched to 75 mg twice daily.

Endpoints for OLE Period:

- Efficacy and CCI endpoints at Week 48, 96, 144, 192, 240, 288, 336 and 384.
 - Number of gadolinium-enhancing T1 lesions;
 - ARR, based on protocol-defined qualified relapses;
 - Qualified relapse-free status;
 - Change from baseline in disability score based on EDSS score;

Safety as assessed by the nature, severity, and occurrence of AEs; vital signs; ECGs; absolute concentrations and change from Baseline in Ig levels;
 ; and clinical laboratory safety parameters.

For the Final Analysis, selected safety and efficacy endpoints based on data from OLE Day 1 to the end of the study will be evaluated.

For more details on the main study objectives please review section 4 Trial Objectives of the protocol.

7 Sample Size/Randomization

Sample size and randomization is described in the IAP for the primary analysis/blinded extension analysis performed after completion of the Double-Blind Period (DBP) of the study (Week 48/Week 52).

8 Overview of Planned Analyses

The protocol describes a total of 5 analyses that should be performed for this study. 4 of them have already been conducted according to the protocol. These are:

- Primary Analysis (when 100% of participants enrolled reached Week 24 of treatment, or prematurely discontinued from treatment)
- Blinded Extension Analysis (when 100% of participants enrolled either reached Week 52 (4-week Safety Follow-up Visit) and completed the study, enrolled in the OLE, or prematurely discontinued from study)
- Safety OLE W60 Interim Analysis (when 100% of participants enrolled in the OLE reached OLE Week 60 or discontinued prematurely from the OLE prior to OLE Week 60)
- OLE W240 Interim Analysis (timed to occur shortly before the primary analysis of the Phase 3 studies in RMS, to support the results of Phase 3 studies)

The last analysis is:

• Final Analysis (triggered when 100% of participants enrolled in the OLE will complete the OLE or will discontinue prematurely from the OLE)

This IAP covers the Final Analysis. Statistical analyses will be performed using cleaned electronic Case Report Form (eCRF) data, lab and MRI data collected up until end of study. All endpoints for the OLE period will be evaluated.

9 Changes to the Planned Analyses in the Clinical Trial Protocol

There are no changes to the planned analyses in the Clinical Trial Protocol (CTP) for the Final Analysis.

10 Protocol Deviations and Analysis Sets

10.1 Definition of Protocol Deviations and Analysis Sets

Important protocol deviations are protocol deviations that might significantly affect the completeness, accuracy, and/or reliability of the study data or that might significantly affect participants rights, safety, or well-being.

The following important deviations will be identified and confirmed prior to or at the Data Review Meeting at the latest.

- Participants who are dosed on the study despite not satisfying the inclusion criteria
- · Participants who develop withdrawal criteria whilst on the study but are not withdrawn
- Participants who receive the wrong treatment or an incorrect dose
- Participants who receive an excluded concomitant medication
- Deviation from Good Clinical Practice
- Inclusion and exclusion criteria violations
- Concomitant medication violations
- Other violations/events that may have a relevant influence on the analysis (e.g., adverse events (AEs), vomiting, sample processing errors, inaccurate dosing, etc.)

Protocol deviations will not lead to the exclusion of a participant from an analysis set for the Final Analysis.

All important protocol deviations should be documented in Clinical Data Interchange Standards Consortium Study Data Tabulation Model (SDTM) whether identified through sites monitoring, medical review and/or programming based on the inclusion/exclusion criteria presented in the protocol. Important protocol deviations are listed and described in the Monitoring Plan-PDMP-28Nov2022.pdf.

10.2 Definition of Analysis Sets and Subgroups

Screening Analysis Set (SCR)

The Screening (SCR) Analysis Set includes all participants who signed the informed consent.

Safety Analysis Set (SAF)

The Safety Analysis Set (SAF) consists of all participants who receive at least one dose of trial treatment. Participants will be analyzed according to the actual treatment they received during the DBP.

Modified Intent-To-Treat Analysis Set (mITT)

The mITT Analysis Set consists of all subjects randomly allocated to a treatment who belong to the Safety Analysis Set, and who have at least one baseline and one post-baseline MRI assessment. Subjects will be analyzed according to the treatment they were randomized to.

Modified Intent-To-Treat Open-Label Extension Analysis Set (mITT-OLE)

The modified ITT OLE Analysis Set (mITT-OLE) Analysis Set consists of all subjects randomly allocated to a treatment who belong to the Safety OLE Analysis Set, and who have at least one MRI assessment on or after OLE Week 0. Subjects will be analyzed according to their planned treatment during the DBP.

Safety Open-Label Extension Analysis Set (SAF-OLE)

The Safety OLE Analysis Set consists of all participants who receive at least 1 dose of Evobrutinib during the OLE. Participants will be analyzed according to the actual treatment they receive during the DBP.

Safety Switch Open-Label Extension Analysis Set (SAF-SWOLE)

The Safety Switch OLE Analysis Set consists of all participants who receive at least 1 dose of Evobrutinib 75 mg BID after a switch of dose from 75 mg QD during the OLE. Participants will be analyzed according to the actual treatment they receive during DBP.

The SAF and mITT analysis sets were pre-defined by the CTP and mainly used for PA/BEA. Specific safety OLE analysis sets (SAF-OLE, SAF-SWOLE) were defined in the IAP for OLE W60 Safety IA (version 1.0, 16Jan2020). The mITT-OLE analysis set was defined in the OLE W240 IA IAP.

The use of the analysis sets in the different analyses is summarized in the following table:

Table 1: Analysis set

Analyses	SCR Analysis Set	SAF Analysis Set	SAF- OLE Analysis Set	SAF- SWOLE Analysis Set	mITT Analysis Set	mITT-OLE Analysis Set
Subject Disposition	✓		✓			
Protocol Deviations			✓			
Demographic and Other Baseline Characteristics			✓			
Previous and Concomitant Medications/Procedures			√			
Treatment Compliance and Exposure			✓	✓		
Efficacy					✓	✓
Safety Evaluation		✓	✓			

11 General Specifications for Statistical Analyses

All statistical analyses will be performed by PPD Inc.

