7.3.1 Brain Magnetic Resonance Imaging Scans

MRI scans will be performed at Screening, at 4-week intervals from Week 12 to 24, and at the End of Treatment Visit at Week 48 (including for participants receiving Tecfidera who choose to enter

the OLE Period). For participants in the OLE Period, an MRI will also be performed at Day 1 (except for participants who received Tecfidera during the 48-week parent study and had an MRI at the End of Treatment Visit at Week 48), Week 48, and then every 48 weeks up to and including the OLE End of Treatment Visit. If a participant discontinues the study more than 4 weeks after his or her most recent MRI, an MRI may be obtained at the 4-week Safety Follow-up Visit. The Screening MRI scan should be acquired before randomization and dosing to allow for the readouts to be read by the central MRI reader (approximately 7 days).

Gadolinium will be used to enhance T1-weighted lesions and to optimize clarity and accuracy of reporting. As gadolinium is excreted renally, participants with acute renal insufficiency (eGFR < 45 mL/min/1.73 m²) will be excluded from the trial (see Section 5.3.2, exclusion criterion 33).

Brain MRI scans will be performed according to a standardized imaging protocol before and after the administration of single-dose gadolinium.

Images will be assessed and reported by an independent, blinded, centralized MRI reading service, provided by PPD.

The assessment will be performed in the absence of clinical information. Further details, including the scans required and the optimal MRI workflow, will be provided in a separate Imaging Manual that will be provided to each trial site by PPD.

All MRI images will be reviewed and reported locally by a radiologist for safety. The local report will contain only nonMS pathology and will be provided to the Treating Investigator.

Note: Where possible, the use of high dose corticosteroids should be avoided in the 3-week period prior to a scheduled MRI scan. In participants receiving corticosteroids for an MS relapse, there must be a 3-week interval between the last dose of corticosteroids and the scheduled MRI scan.

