8.4 Analysis Sets

For the purposes of analysis, the following analysis sets are defined:

Safety Analysis Set

The Safety Analysis Set consists of all participants who receive at least 1 dose of trial treatment. Participants will be analyzed according to the actual treatment they receive.

Intent-To-Treat Analysis Set

[figure not shown]
The Intent-To-Treat ITT Analysis Set consists of all participants randomly allocated to a treatment, based on the intention to treat "as randomized" principle (i.e., the planned treatment regimen rather than the actual treatment given in case of any difference).

Modified Intent-To-Treat Analysis Set

The mITT Analysis Set consists of all participants who belong to both the ITT and Safety Analysis Sets, and who have at least one baseline and one postbaseline MRI assessment.

Per-Protocol (PP) Analysis Set

The PP Analysis Set consists of all participants who belong to the mITT Analysis Set, complete 24 weeks of treatment, and do not have any important protocol deviations.

Open-Label Extension Analysis Set

The OLE Analysis Set consists of all participants who receive at least 1 dose of M2951 during the OLE.

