If the subject didn't switch the dose, $\frac{(N_{1as})}{6*N_{2as}}$ is set to 0. If a kit is received by the participant but no information about the number of tablets returned is available because of lost to follow-up, the kit is not considered in the calculation of compliance.

Compliance with treatment will be presented by summary statistics during the OLE period and according to the categories < 60%, $\ge 60\%$ to < 80%, $\ge 80\%$ to < 90%, $\ge 90\%$ to < 110%, $\ge 100\%$. For this analysis the SAF-OLE analysis set will be used. Tables about compliance before or after the switch during OLE period will be also provided. Tables after the switch will be restricted to SAF-SWOLE Analysis Set.

The following listings will be provided:

- listing of Evobrutinib start/end dates of the single administration with number of ingested tablets (from EXPOSUREDT3 eCRF page), for the study drug administration during the OLE period.
- listing with exposure time, cumulative dose, and compliance during the OLE period.

16 Efficacy Evaluation

All efficacy analyses will be based on the mITT and mITT-OLE analysis sets, as specified in below sections. All analyses are descriptive, there is no hypothesis testing.

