16.2 Relapses

Annualized Relapse Rates (ARR)

Descriptive statistics on relapses during the OLE period will be provided by treatment group and overall on the mITT-OLE analysis set. In particular, at the treatment-group-level, number of qualified relapses, total number of relapses (qualified or not), follow-up on treatment (in participant-years), and unadjusted ARR based on protocol-defined qualified relapses (number of qualified relapses divided by follow-up on treatment) and confidence intervals will be reported. In addition, descriptive statistics of participant-level ARR (number of qualified relapses experienced

by a participant, divided by the follow-up experienced by a participant) will be summarized for each treatment group, in terms of mean, SD, median, Q1, Q3, min, and max.

Subjects discontinuing early are analyzed according to number of years of follow-up on treatment and number of qualified relapses observed at the time of discontinuation, including data (both follow-up time and number of relapse events) from the 4-week Safety Follow-up period.

The summary will be presented for the overall OLE period (OLE Baseline – last OLE visit), for each 48-week period during the OLE, between OLE Baseline and Dose Switch during OLE, and between Dose Switch during OLE to the last OLE visit.

A listing will be provided for relapse data, by participant for the DBP and OLE treatment period combined.

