16.3 Time to First Qualified Relapse and estimates

Time to first qualified relapse will be represented by a Kaplan-Meier (KM) plot on the mITT for the DBP + OLE period with orientation "increasing left to right", and with labels "Time from randomization (Weeks)" vs "Cumulative probability of qualified relapse". 1 curve will be provided for each of the 5 treatment groups. The cumulative probability of an event is estimated with PLOTS=SURVIVAL(FAILURE) option of PROC LIFETEST.

The horizontal axis should extend as far as needed to include follow-up from all participants, regardless of whether the time to an event is observed or censored.

A qualified relapse event will be counted even if it occurs after the participant has discontinued treatment.

Participants who have qualified relapse during DBP + OLE period, will have the time to first qualified relapse (weeks) calculated as "([date of first qualified relapse] – [date of first dose] + 1)/7".

Participants who do not have qualified relapse, or are lost to follow up, will be censored at the date of the last relapse assessment for this analysis. The censoring time (weeks) will be calculated as "([date of censoring] – [date of first dose] + 1)/7".

KM estimates (product-limit estimates) of the cumulative probability of experiencing qualified relapse over time will be presented in a table by treatment group, together with a summary of percentiles (5th, 10th, 15th, 20th, 25th, 30th, 35th, 40th, median) and corresponding 2-sided 95% CIs, as well as number of participants at risk, number of participants with an event, number of censored participants.

Number and percentage of subjects with qualified relapse-free status will be provided by treatment group and overall.

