16.4 Expanded Disability Status Scale (EDSS)

Descriptive statistics for the EDSS score and EDSS CFB at each visit during the DBP and the OLE period combined will be provided by treatment group and overall on the mITT analysis set.

In addition, descriptive statistics for the EDSS score and EDSS CFB at each visit during the OLE period only will be provided by treatment group and overall on the mITT-OLE analysis set (early treatment discontinuers during OLE will be presented at 'EOT' visit).

Descriptive statistics for categorical EDSS CFB, i.e., number and proportion improving, stable, or worsening, will also be reported for each time point. Here improvement is defined as a decrease of 1.0 point or more, stable condition as a change of no more than half a point in either direction and worsening as an increase of 1.0 point or more.

Mean CFB in EDSS will be presented on mITT analysis set as a by-year line plot during DBP and OLE period combined. The plot will be provided for each treatment group and overall, with a vertical line segment at each visit representing \pm SE (jittered if needed for legibility), and with all treatment groups included in a single figure.

Additionally, the plot of mean CFB in EDSS will be presented for OLE period only (OLE Week 48 to OLE Week 336 and EOT) on mITT-OLE analysis set.

A listing will be provided for EDSS data, by participant and by timepoint for the DBP and OLE treatment period combined.

17 Safety Evaluation

The subsections in this section include specifications for summarizing safety endpoints that are common across clinical trials such as adverse events, laboratory tests and vital signs.

All outputs will be provided on the OLE period if not otherwise indicated.

Safety analyses will be based on the SAF for summaries on the DBP + OLE period and on the SAF-OLE for summaries on the OLE period, according to the as-treated principle.

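### The OLE relapse-rate and OLE-only EDSS summaries require an MRI that neither outcome needs, and the SAP leaves unclear whether the former Tecfidera arm's Week 48 scan satisfies that condition.

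*SAP*

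**What the plan says.** **Set definition.** SAP 10.2 builds mITT-OLE from randomised members of the Safety OLE set "who have at least one MRI assessment on or after OLE Week 0". Participants are analysed by planned double-blind treatment.

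**Use of the set.** SAP 16 states: "All efficacy analyses will be based on the mITT and mITT-OLE analysis sets". Under 16.2: "Descriptive statistics on relapses during the OLE period will be provided by treatment group and overall on the mITT-OLE analysis set". Under 16.4, EDSS at "each visit during the OLE period only will be provided by treatment group and overall on the mITT-OLE analysis set".

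**Outputs on a different set.** Time to first qualified relapse is "represented by a Kaplan-Meier (KM) plot on the mITT for the DBP + OLE period" (16.3). The count of relapse-free participants sits in the same section, which names no other set. EDSS at "each visit during the DBP and the OLE period combined will be provided by treatment group and overall on the mITT analysis set" (16.4). The mITT set needs no OLE scan.

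**Scan schedule.** Protocol 7.3.1 requires an OLE Day 1 MRI, "except for participants who received Tecfidera during the 48-week parent study and had an MRI at the End of Treatment Visit at Week 48". Participants coming from evobrutinib or placebo have their Week 48 visit treated as OLE Day 1 (footnote to Protocol Figure 2), and Table 2 schedules an MRI there.

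**Protocol set.** In Protocol 8.4, "The OLE Analysis Set consists of all participants who receive at least 1 dose of M2951" in the extension, with no MRI condition. Protocol 8.5.4.3 leaves the OLE efficacy details to the IAP.

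**The concern.** Relapse counts, follow-up time and EDSS are recorded whether or not a scan is done. An MRI condition on these outcomes can only remove people, and it removes their events and person-time with them.

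The scan schedule makes the condition uneven across arms. Participants from evobrutinib or placebo normally meet it on the day they enter the OLE. Former Tecfidera participants with a Week 48 scan had that scan before a washout of at least four weeks (Protocol 5.5.1). By calendar date, their next scheduled scan is at OLE Week 48, or at OLE End of Treatment if they stop sooner. Their membership would then depend on something that happens after entry.

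A missing scan could also be related to outcome. Protocol 7.3.1 requires three weeks between the last corticosteroid dose for a relapse and a scheduled MRI. Protocol 5.6.1 asks anyone stopping therapy to come at once for the End of Treatment Visit. Someone treated for a relapse who then stops could plausibly have no scan at that visit, and the later follow-up scan is optional.

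This would work against SAP 16.2 itself, which says early discontinuers contribute their follow-up and qualified relapses up to discontinuation, including the safety follow-up period.

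**Working it through.** **Step 1. Size of the group.** Protocol 8.1 gives about 250 participants and 80% continuation: 250 × 0.80 = 200, the stated OLE size. With 1:1:1:1:1 randomisation and equal continuation across arms (assumed), 200 / 5 = 40 come from Tecfidera.

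**Step 2. Does the Week 48 Tecfidera scan count?**

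- *By calendar date:* no. It precedes OLE Day 1 by the washout.
- *By analysis visit:* yes. SAP Appendix 3 assigns MRI from main-period day 189 up to, but not including, OLE day 30 to OLE Week 0 for all treatment groups. The Week 48 visit is day 336 ± 3, so days 333 to 339 all fall inside.

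SAP 11.13 introduces the windows for by-visit summaries and does not mention set membership. SAP 10.2 does not cite Appendix 3. The text does not settle the question.

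**Step 3. How many could be lost on the calendar-date reading?** The documents give no OLE dropout rate. As an assumption, take the main-study planning value of 12% per year (Protocol 8.1) up to OLE Week 48 (day 336):

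- Share leaving before day 336: 1 − 0.88^(336/365.25) = 0.111
- Leavers: 40 × 0.111 = 4.4

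Leavers are due an OLE End of Treatment Visit (Protocol 7.1.6), where Table 3 schedules an MRI. Only those without that scan, or any other OLE scan, are lost:

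| Assumed share of leavers with no OLE scan | Lost from mITT-OLE |
|---|---|
| 0% | 0 |
| 25% | 4.4 × 0.25 = 1.1 |
| 50% | 4.4 × 0.50 = 2.2 |
| 100% | 4.4 |

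**Step 4. The analysis-visit reading.** The Week 48 scan satisfies the condition, and the number lost for this reason is 0.

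**Step 5. Other arms.** Protocol 7.3.1 allows a scheduled scan to be cancelled to space gadolinium exposures. A participant from any arm whose Day 1 scan was missed or cancelled, and who left without a later scan, would also be excluded. Conversely, a former Tecfidera participant with no Week 48 scan is not exempt from the Day 1 scan.

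**The case against.** The strongest reply is that Appendix 3 already solves the problem. Its MRI window covers all treatment groups, whereas the immunoglobulin and immune-cell windows give the Tecfidera arm its own OLE Week 0, limited to OLE Day 1. The difference looks deliberate, and it fits a protocol that waives the Day 1 scan because a Week 48 scan exists. SAP 10.2 uses the same visit label. This may well be the intended reading, but the SAP does not state it. If it is right, the MRI condition does almost nothing for these outcomes, so removing it from them loses nothing.

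Other points also stand:

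- Early leavers are due an End of Treatment MRI, and a further scan may be obtained at safety follow-up. Loss requires all of these to be missing. However, SAP 15 has a rule for participants lost to follow-up without an End of Treatment visit, so the SAP foresees that case.
- Relapse alone is not a reason to withdraw (Protocol 6.4.1 and 7.3.3), which weakens the link between relapsing and leaving.
- All efficacy analyses are descriptive, with no hypothesis testing. Relapses are also listed by participant across both periods, and listings default to SAF-OLE, so events would remain visible.

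A reader might infer that the SAP contradicts the protocol. The documents do not support that. Protocol 8.4 does not assign its OLE Analysis Set to efficacy, and 8.5.4.3 defers to the IAP. Protocol 8.5.3 itself analyses the main-study secondary endpoints, including ARR and EDSS, on an MRI-conditioned mITT set. What remains is narrower: mITT-OLE is an additional set taken from the Week 240 interim IAP (SAP 10.2), while SAP section 9 reports no changes.

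**Conclusion.** The point holds as an unnecessary and ambiguous condition on two outputs: the OLE relapse and ARR summary, and the OLE-only EDSS summary. On the calendar-date reading it can remove early leavers, mainly from the former Tecfidera arm. On the analysis-window reading it removes almost nobody. Time to first relapse, relapse-free status and EDSS over both periods combined are unaffected.

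The size is unknown. The range of about 0 to 4 of 40 rests on equal continuation across arms, 12% annual dropout carried into the OLE, and assumed shares of missing scans.

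A reader might infer that the former Tecfidera ARR is seriously understated. For example, suppose 3 of 40 are lost, each with one relapse in 0.3 years, and the rest relapse at 0.12 per year over 0.92 years. Then 37 × 0.92 = 34 person-years carry 4.1 relapses, an ARR of 0.12. Restoring the three gives 7.1 / 34.9 = 0.20. The documents supply none of these inputs, and the example gives the lost participants 3 / 0.9 = 3.3 relapses per year, about 28 times the assumed rate. With one such participant lost, 39 × 0.92 = 35.9 person-years carry 4.3 relapses, and restoring that person gives 5.3 / 36.2 = 0.15. If leavers relapse at the common rate, the ARR does not move. The documents show that bias is possible, not that it is large.

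**What to change.** 1. In SAP 16.2 and 16.4, run OLE ARR and OLE-only EDSS on all participants with at least one OLE dose. SAF-OLE already has this population, with the same dosing definition as the protocol's OLE Analysis Set. Present results by randomised arm; SAF-OLE is otherwise grouped by actual treatment, so this needs stating.
2. Keep mITT-OLE for the MRI endpoints. State in SAP 10.2 whether OLE Week 0 means the calendar date or the Appendix 3 analysis visit, and so whether the Tecfidera Week 48 scan counts.
3. Record mITT-OLE in SAP section 9 as an addition to the protocol's analysis sets.

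The cost is a few lines of text and a rerun of the affected tables and the OLE-only EDSS plot. No new data are needed, and every dosed participant's observed relapses and follow-up are kept on either reading.
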